4.8 OTHER ANALYSES

4.8.1 *Immunogenicity analyses*

Anti-rhGAA IgG Binding Antibody

Participant's ADA status, response variable, and kinetics of ADA responses (see definitions below) will be summarized for all patients with available ADA data.

Kinetics of ADA response

Kinetics of ADA response will be derived for patients ever ADA positive, whether with ADA already present at baseline or seroconverted during the study. Time to ADA onset (seroconversion) and time from seroconversion to first peak titer will be described with mean, SD, median, Q1, Q3, minimum, and maximum statistics.

- **Persistent ADA response** is defined as ADA positive at the last sample timepoint and meets one of the following two criteria:
 - ADA positive at two or more sampling time points post baseline, where the first and the last ADA-positive post-baseline samples (irrespective of any negative sample in between) are separated by at least 16 weeks; or
 - ADA positive at last two sampling time points, irrespective of the time in between.
- **High ADA response** is a subcategory of persistent ADA response and identifies a patient who was persistently seropositive positive, had a peak titer ≥ 12800 , and was seropositive at final assessment.
- **Tolerized ADA response** is a subcategory of persistent ADA response and identifies a patient who was persistently seropositive, but seronegative at the final assessment.

The following definitions will also be used:

- **ADA peak titer** (highest ADA titer from first study infusion of alglucosidase alfa) for ever positive patients.
- **Time to ADA seroconversion from first alglucosidase alfa infusion in study**

Time to seroconversion (days) from 1st alglucosidase alfa infusion in study will be calculated by (date of seroconversion - date of 1st alglucosidase alfa infusion in study + 1)

- **Time to first alglucosidase alfa ADA peak titer from seroconversion**

Time to first peak titer (weeks) from seroconversion will be calculated by (date of first peak titer - date of seroconversion + 1) / 7

- **ADA peak titer category** (always negative, 100-800, 1600-6400, ≥ 12800).
- **Last ADA titer** (final assessment after first study infusion of alglucosidase alfa) for ever positive patients.
- **ADA last titer category** (≤ 800 , 1600-6400, ≥ 12800).

Titer values will be presented using descriptive statistics (number, geometric mean [GM], geometric SD, median, Q1, Q3, minimum, and maximum, as well as by number and percentage in titer categories). ADA titer values over time for individual patients will also be presented graphically.

Please refer to [Section 5.4.1](#) for the handling of ADA data.

Neutralizing ADA (inhibitory antibody) Status

Neutralizing ADA antibodies (NAbS that inhibit enzyme activity and NAbS that inhibit cellular uptake) measured during the study will be presented in a listing.

Additional Testing For Moderate or Severe IARs

Results of circulating immune complex, IgE antibody, serum tryptase, complement activation testing, and skin testing results will be presented in data listings.

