- Any TEAE leading to treatment interrupted
- Any TEAE leading to permanent intervention discontinuation
- TEAE leading to death

The AE summaries of [Table 5](#) will be generated with event count and number (%) of patients experiencing at least one event.

Table 5 - Analyses of adverse events

Type of AE	MedDRA levels
All TEAEs	Primary SOC and PT
TEAEs related to IMP	Primary SOC and PT
TEAEs by maximal severity	Primary SOC and PT
Related TEAEs by maximal severity	Primary SOC and PT
Treatment emergent SAEs	Primary SOC and PT
Treatment emergent SAEs related to IMP	Primary SOC and PT
TEAEs leading to permanent intervention discontinuation	Primary SOC and PT
TEAEs leading to death (death as an outcome of the AE as reported by the Investigator in the AE page)	Primary SOC and PT
Pretreatment AE	Primary SOC and PT

Subgroup analysis

TEAEs stratified by the following categories will also be presented by primary SOC and PT:

- Status of high ADA response (with, without)
- Seroconversion status (negative, positive) and peak ADA categories for those who seroconverted

Analysis of deaths

A listing of patients who died during the study will be provided.

Analysis of infusion-associated reactions (IARs) and other AEs of interest

Protocol-defined IARs

Infusion-associated reactions (IARs) are defined as AEs that occur during the infusion or within up to 24 hours after the start of infusion and are considered as related or possibly related to the ERT by the Investigator or the Sponsor. At the discretion of the Investigator, AEs occurring ≥ 24 hours after the start of the infusion that are assessed as related may also be considered IARs.

Algorithm-defined IARs

An alternative definition of IAR which does not rely on the investigators' assessments of an AE's relationship to the treatment will also be employed. It includes potential IARs (all AEs occurring during an infusion or within 2 hours after the completion of an infusion; and all AEs occurring from >2 to 24 hours after the completion of an infusion).

Protocol-defined infusion-associated reactions and algorithm-defined potential IARs will be selected for analyses as indicated in [Table 6](#). Number of events and number (%) of patients experiencing at least one event will be provided for each event of interest for the IARs. Tables will be sorted as indicated in [Table 4](#).

Anaphylactic/hypersensitivity reactions and immune-mediated reactions

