5.4 APPENDIX 4 DATA HANDLING CONVENTIONS

5.4.1 Derivations

The following formulas will be used for computation of parameters:

Age (months) at signing of informed consent = (date of informed consent - date of birth + 1)/30.4375

Age (months) at first alglucosidase alfa infusion = (date of first infusion - date of birth + 1)/30.4375

Age (months) at Pompe diagnosis = (date of Pompe diagnosis - date of birth + 1)/30.4375

Age (months) at first Pompe symptom = (date at first Pompe symptom - date of birth + 1)/30.4375

Time (months) from first Pompe symptom to first alglucosidase alfa infusion = (date at first infusion - date at first Pompe symptom + 1)/30.4375

Time (months) from Pompe diagnosis to first alglucosidase alfa infusion = (date at first infusion - date at Pompe diagnosis + 1)/30.4375

BMI = weight [kilograms] /(height [meters])²

Computation of Z-scores (standardized age and gender adjusted values) and percentiles for height/length, weight, and head circumference will be according to Center for Disease Control (CDC) growth Charts(1) and World Health Organization (WHO) growth charts(2). The WHO growth charts are recommended for children <24 months of age.

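### Does the missing seroconversion date for patients already ADA positive at baseline undermine the ADA time summaries or the TEAE table by seroconversion status?

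*SAP*

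**What the plan says.** SAP 4.8.1 sets the population for the kinetics: "Kinetics of ADA response will be derived for patients ever ADA positive, whether with ADA already present at baseline or seroconverted during the study". The statistics follow at once: "Time to ADA onset (seroconversion) and time from seroconversion to first peak titer will be described with mean, SD, median", together with quartiles and range. Time to seroconversion, in days, is "date of seroconversion - date of 1st alglucosidase alfa infusion in study + 1". Time to first peak, in weeks, is ("date of first peak titer - date of seroconversion + 1) / 7". Peak titer is the "highest ADA titer from first study infusion of alglucosidase alfa" and is defined for ever-positive patients.

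SAP 4.7.2 also plans TEAE tables by "Seroconversion status (negative, positive) and peak ADA categories for those who seroconverted".

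SAP 4.8.1 sends the reader to 5.4.1 "for the handling of ADA data". That section opens with "The following formulas will be used for computation of parameters" and lists ages, intervals, BMI and growth scores, with nothing on ADA. The ADA text is in 5.4.2 and covers only titers reported as below a limit and missing titers. SAP 5.4.5 adds that continuous variables are summarized from the values observed.

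**The concern.** Both formulas need a date of seroconversion, and the population expressly includes children who were positive before the first study infusion. For them no earlier negative sample bounds the onset. A programmer could enter the baseline sample date, enter the first positive post-baseline sample date, or leave the value missing.

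The situation is foreseeable. Protocol 7.1 admits children aged 1 year to 24 months only if treatment has already begun, and SAP 5.4.3 gives a maximum age at consent of 1.9 years. At least one of the 12 enrolled patients was therefore pre-treated, if eligible. Anti-rhGAA IgG formation is among the secondary endpoints in SAP Table 2.

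At stake would be a minimum onset time near zero that describes no real onset, a time to peak that moves by about 13 weeks with the convention chosen, and an antibody-positive child possibly counted as negative in a safety table.

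**Working it through.** The plan gives no ADA figure to reproduce, so the check applies its two formulas and then compares the texts.

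**Inputs.** Day 0 is the first study infusion (notes to the window tables, SAP 5.4.3). The baseline IgG sample is taken just before that infusion (protocol 9.1.1), or on Day -30 to -1 (SAP Table 10). The first post-baseline sample is at Month 3, target Day 91 (SAP Table 10). With the 60-day window of protocol 9.1 it falls on Day 31 to 151. Enrolled: 12 (SAP 5.2). Number positive at baseline: not given.

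**Time to seroconversion for one baseline-positive child** (sample day - 0 + 1):

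- Baseline sample date: Day 0 gives 1; Day -1 gives 0; Day -30 gives -29 days.
- First positive post-baseline sample: 91 + 1 = 92 days (32 to 152 across the window).
- No conversion in the study: missing.

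**Time to first peak, peak assumed at Day 365** ((peak day - seroconversion day + 1)/7):

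- Baseline date, Day 0: 366/7 = 52.3 weeks.
- Post-baseline date, Day 91: 275/7 = 39.3 weeks.
- The difference is 91/7 = 13.0 weeks. It becomes 92/7 = 13.1 with a Day -1 baseline sample and 121/7 = 17.3 with Day -30.
- No conversion: missing.

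**Effect on the mean onset time.** Assume all 12 patients are ever positive, k of them at baseline (sampled on Day 0), and the rest convert at 92 days.

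| k | Baseline date | Post-baseline date | Missing |
|---|---|---|---|
| 1 | (11×92 + 1)/12 = 84.4 | 92, n = 12 | 92, n = 11 |
| 3 | (9×92 + 3)/12 = 69.25 | 92, n = 12 | 92, n = 9 |
| 6 | (6×92 + 6)/12 = 46.5 | 92, n = 12 | 92, n = 6 |

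Only the first column moves. The second stays at 92 by construction, because every patient is set to 92 days. None of the assumptions is in the documents.

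**Which reading does the text support?** The population sentence names two groups: those with ADA present at baseline and those who seroconverted during the study. A child in the first group has, in the sentence's own terms, no conversion in the study and so no date for the formula. Entering the baseline date would place a conversion counted from the first study infusion at or before that infusion. With the date absent, SAP 5.4.5 leaves the child out of both time summaries. Including such children in the section still has a purpose, because persistent response, high response, peak titer and last titer need no seroconversion date.

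**TEAE table.** Both dated readings class a baseline-positive child as positive, so they give the same table. Only the missing-date reading could move the child to negative or out of the table. Against that, the peak-titer categories in 4.8.1 begin with a class for patients who are always negative, and peak titer is defined for ever-positive patients. This points to negative meaning never positive, which keeps the child on the positive side. Each patient is 1/12 = 8.3% of those enrolled.

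**The case for a change.** The strongest case for a change is that the sentence says kinetics will be derived for baseline-positive children, and the next sentence does not limit the time variables to converters. The favored reading also uses the term in two senses: no conversion event for the times, but positive status for the TEAE table. The SAP states neither. Version 2.0 revised the immunogenicity section, the remedy would be a few sentences and one flag from data already held, and without a rule the choice may be made after the data are seen.

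The absence of a definition, the double use of the term and the wrong cross-reference all stand. The claim of distortion does not. Prior treatment in at least one child is shown; ADA positivity at baseline is not shown for any child. The numerical shifts depend on the reading the text supports least. The outputs are descriptive with no testing planned, and no decision rule uses these times. With 12 enrolled patients and individual titer curves planned in 4.8.1, a reader can see who was positive at the start and how the child was handled.

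**Conclusion.** No change to the plan is needed. This is an unwritten definition that an analyst can fill from the surrounding text: seroconversion is a change from negative at study baseline to positive later, dated at the first positive sample. Baseline-positive children have no value for the two times but keep their peak and last titers, and they count as positive in the TEAE table. On that reading the only effect is a smaller n in two descriptive summaries, by the number positive at baseline. That number is not given and may be zero, so no numerical distortion can be claimed. The reference in 4.8.1 to 5.4.1 is a clerical slip for 5.4.2.

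The conclusion rests on two assumptions: that the programmer respects the sentence's contrast between the two groups, and that the individual titer plots are produced as planned. If a baseline date were used instead, an onset time at or below 1 day would show in the reported minimum and could be traced to the patient.

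### SAP 4.8.1 makes the Tolerized ADA category impossible to enter, so the summary must report zero tolerized patients whatever the data show

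*SAP*

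**What the plan says.** SAP Section 4.8.1 plans that "kinetics of ADA responses (see definitions below) will be summarized for all patients with available ADA data". The definitions that matter are these:

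- **Persistent** "is defined as ADA positive at the last sample timepoint and meets one of the following two criteria". Criterion 1 asks for at least two positive post-baseline samples, the first and last of them 16 weeks or more apart. Criterion 2 is "ADA positive at last two sampling time points, irrespective of the time in between".
- **High** is a subset of Persistent with a peak titer of at least 12800. It repeats the requirement of a positive final sample.
- **Tolerized** "is a subcategory of persistent ADA response and identifies a patient who was persistently seropositive, but seronegative at the final assessment".
- **Last ADA titer**, for patients who were ever positive, is the "final assessment after first study infusion of alglucosidase alfa". Its bands are ≤800, 1600-6400 and ≥12800.
- **Peak titer category** has the levels "always negative, 100-800, 1600-6400" and ≥12800.

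Section 4.8.1 then sends the reader to Section 5.4.1 "for the handling of ADA data". Section 5.4.1 contains no ADA rule. The one that exists is in Section 5.4.2: a titer reported as below a limit takes the limit value in summaries, with <100 becoming 100 as the example.

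**The concern.** Persistent requires a positive last sample, and Tolerized is a part of Persistent that requires a negative one. If the two phrases mean the same sample, nobody can be Tolerized.

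Anti-rhGAA IgG formation is one of the secondary endpoints in SAP Table 2. Programmed literally, its summary shows zero tolerized patients, and a reader could take that zero as a finding. If the programmer instead adopts the apparently intended meaning without saying so, the output departs from the SAP with no record. SAP Section 5.2 reports 12 enrolled patients, so one misclassified patient is 1/12 = 8.3% of the cohort.

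The last-titer table is the other place where loss of antibody might appear as a summary category, and it has no negative level either.

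**Working it through.** **Are the two samples the same?** Section 4.8.1 uses the term final assessment for the last titer after the first study infusion. Section 5.4.4 counts unscheduled ADA samples in the last on-treatment value, so a later unscheduled sample does not create a second kind of last sample. Nothing in the SAP separates the two terms.

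**Logic.** Let C1 and C2 be the two criteria and L a positive last sample.

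- Persistent = L and (C1 or C2).
- Tolerized = Persistent and not L, which is empty.
- C2 already implies L. The lead-in condition therefore acts only on C1, where it removes exactly the patients with C1 and not L, the group that Tolerized describes.

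**How many response patterns lose their label.** The inputs are the 16 post-baseline target days in SAP Table 10: 91, 183, 274, 365, 456, 548, 639, 731, 1096, 1461, 1826, 2192, 2557, 2922, 3287 and 3653. The C1 threshold is 16 × 7 = 112 days.

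Take a patient with k visits, the last of them negative. At least one of the other k − 1 visits is positive in 2^(k−1) − 1 patterns. C1 then fails in only two ways:

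- There is a single positive sample: k − 1 patterns.
- There are exactly two positives at neighbouring visits less than 112 days apart. Gaps among the first eight visits are 91 or 92 days; the next gap is 1096 − 731 = 365 days. This gives 6 patterns for k = 8 and 7 for k = 10 or 16.

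| Follow-up ends at | Patterns | Ever positive, last negative | C1 fails | C1 met, last negative: no label | Tolerized as written |
|---|---|---|---|---|---|
| Month 24 (8 visits) | 256 | 127 | 7 + 6 = 13 | 114 | 0 |
| Month 48 (10 visits) | 1,024 | 511 | 9 + 7 = 16 | 495 | 0 |
| Month 120 (16 visits) | 65,536 | 32,767 | 15 + 7 = 22 | 32,745 | 0 |

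These agree with a direct enumeration of every pattern. They count possible sequences and say nothing about how many patients will follow them.

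**Persistent, for comparison.** With 16 visits, 32,768 patterns end positive. Only the one whose sole positive is the last sample fails both criteria, which leaves 32,767 Persistent.

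**Example.** A patient positive at all 15 visits from day 91 to day 3287 has positives spanning (3287 − 91)/7 = 456.6 weeks, against the 16 required. If day 3653 is negative, the patient is neither Persistent nor Tolerized.

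**Effect of a repair.** Dropping L from Persistent gives Tolerized = (C1 or C2) and not L. Defining Tolerized separately gives C1 and not L. C2 and not L never occurs, so the two sets are identical: 32,745 patterns with 16 visits. High carries its own positive-final condition and does not change.

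**Last-titer bands.** If negatives are reported as <100, Section 5.4.2 sets them to 100, the bottom of the lowest positive peak band. They fall in ≤800 with the low positives, and the minimum titer does not separate them either.

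**The case against.** The strongest reply is that this is a drafting slip with an evident meaning. The SAP describes the tolerized patient in words, High would not need to repeat the positive-final condition if Persistent already carried it, and both repairs yield the same set. A sensible programmer would probably get it right. That is fair as to intent, but it is an inference. It also leaves open whether the Persistent count should include tolerized patients, which changes a reported number.

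A second reply is that loss of antibody stays visible: ADA titers are plotted for each patient, listings are planned, and with 12 enrolled patients every reversion can be read directly. This stands and limits the harm. Likewise, the adverse event subgroups in Section 4.7.2 use high ADA response, seroconversion and peak titer, so nothing downstream depends on Tolerized.

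Third, the missing negative level is partly preference. The peak level for patients who were always negative means never positive, so it is not a true parallel to a last-titer table restricted to ever-positive patients. The open-ended ≤800 band may be meant to absorb negatives. That also stands: adding the level is a refinement. It matters here because, with Tolerized empty, no other summary category separates these patients from low positives.

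Finally, the pattern counts can look larger than the problem. Section 5.2 says that 7 of the 12 patients had withdrawn or died in less than 4 years, so at most 5 could approach a 16-visit series, and the documents do not show that any patient reverted. The shorter schedules in the table are the more relevant ones; they give zero as well.

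**Conclusion.** The definitions contradict each other, and nothing in the protocol or SAP reconciles them. Tolerized contains no patient under any data. The contradiction does not depend on the counts; they only show that the excluded group is a wide class of response histories (114 of 256 possible patterns at Month 24, 495 of 1,024 at Month 48).

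The conclusion assumes that the last sample and the final assessment are one sample, as the SAP's own usage indicates. The counts assume sampling on the Table 10 target days. The pooling of reverted patients in the ≤800 band assumes that negatives are reported as <100, which the SAP gives only as an example.

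The consequence is limited to the Persistent and Tolerized rows and the last-titer table of a descriptive summary. It should be corrected, because a stated rule forces a zero into a planned summary of a secondary endpoint and the correction is cheap.

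**What to change.** Choose one of two repairs and state which meaning of Persistent applies:

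- **(a)** Delete the last-sample condition from the Persistent definition and keep the two criteria. Final status is then set only in High (positive) and Tolerized (negative), and Persistent includes tolerized patients.
- **(b)** Keep Persistent as it is and define Tolerized as a separate category: criterion 1 met and last sample negative.

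In the same revision, add a negative level to the last-titer category, and change the ADA-handling reference in Section 4.8.1 from Section 5.4.1 to Section 5.4.2.

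The cost is one clause, one category level, one cross-reference and a small programming change.

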4.8.2 Cross-reacting immunologic material (CRIM) status and GAA mutation analysis

CRIM status and GAA mutation are endpoints for research purposes only. (Refer to protocol Sections 9.2.4 and 9.2.5 for their definitions and measurement details.) The collected data will be displayed in a patient listing.

4.9 INTERIM ANALYSES

Not applicable. No interim analysis is planned.

5 SUPPORTING DOCUMENTATION

5.1 APPENDIX 1 LIST OF ABBREVIATIONS

AE:	adverse event
ALT:	alanine aminotransferase
AST:	aspartate aminotransferase
Bayley-III:	Bayley Scales of Infant and Toddler Development
BUN:	blood urea nitrogen
CDC:	Center for Disease Control
CK:	creatine kinase
CK-MB:	creatine kinase MB
ECG:	electrocardiogram
e-CRF:	electronic case report form
GM:	geometric mean
GMFM-88:	Gross Motor Function Measure
HEENT:	head, eyes, ears, nose, and throat
HLT:	high level term
IAR:	infusion-associated reaction
Leiter-3:	Leiter International Performance Scale - 3rd Edition
Leiter-R:	Leiter International Performance Scale - Revised
LLOQ:	lower limit of quantitation/detection limit
LLT:	lower-level term
LVH:	left ventricular hypertrophy
MedDRA:	medical dictionary for regulatory activities
NAb:	neutralizing antibody
PCSA:	potentially clinically significant abnormality
PE:	physical examinations
PEDI:	Pediatric Evaluation of Disability Inventory
PT:	preferred term
RVH:	right ventricular hypertrophy
SAP:	statistical analysis plan
SD:	standard deviation
SGOT:	serum glutamic oxaloacetic transaminase
SGPT:	serum glutamic pyruvic transaminase
SM:	study manual
SOC:	system organ class
TEAE:	treatment-emergent adverse event
ULOQ:	upper limit of quantification
WHO:	World Health Organization
WHO-DD:	World Health Organization-drug dictionary

